Experimental arrangements before experiment Procedure: All subjects will come to the Sharp & Children's MRI Center between 6 and 7 am (or 3 hours prior to the start of the scan). Subjects will have a urine pregnancy test (Study Visit 1 only), and all will receive a standardized breakfast and complete scan day questionnaires.

Taste fMRI – Expected and Unexpected sweet stimulus: In this study, subjects will get small samples (1.0 cc) of fluid that will consist of Sucrose or neutral solution (artificial saliva). These fluid samples will be administered through food grade polyethylene plastic tubes (1/8 inches inner, 3/16 inches outer diameter, FDA/USDA approved, Cole-Parmer, Vernon Hill, IL) that subjects hold in their mouth. In addition, the subjects will be trained to perform one tongue motion after each application of taste stimulant in order to wash the taste stimuli around the mouth and stimulate taste buds. The fluid will be released, at intervals, by a pump mechanism. Because of the small volume of fluid, there is no danger of aspiration. The subjects will be able to swallow the small amounts of solutions after application. Subjects that are not capable of carrying out these required procedures will be excluded from the study.

[figure not shown]
Syringe Pump Assembly: Fluid challenges will be delivered to the subject by an apparatus (Figure 3.1.) that will use a semi-automatic and programmable customized syringe pump (J-Kem Scientific, St. Louis, MO). The syringe pump will pump samples from 5 reservoirs through FDA approved food grade teflon tubes (Cole-Parmer, Vernon Hills, IL; see above) into the subject's mouth. The reservoir tube and the tube to the subject are connected via a 2 way Teflon valve enabling the syringe pump to draw solution from the desired reservoir into the glass syringes that are part of the syringe pump mechanism. The valve at the syringe pump will switch

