This design will be closely modeled after the design used by O'Doherty et al (O'Doherty et al., 2003). Each trial will consist of the presentation of one of five arbitrary visual stimuli (which will be abstract fractals, see Figure 3.2; we established contact with O'Doherty's group and received fractals originally used in this paradigm) followed 3 s later by either 1 ml of a pleasant sweet taste (1 M sucrose) (CS+), a neutral taste (CSneut: 25mM KCl, 2mM NaHCO₃, (Francis et al., 1999, Frank et al., 2003)) or no taste (CS-). The visual stimuli will be presented on a gray background and will be removed from the screen after 3 s to coincide with taste delivery. A fixation cross will then be presented for the remainder of the trial. After a further 3 s, the next trial will be scheduled. The allocation of each stimulus to a given trial type will be counterbalanced across subjects. There will be a total of 280 trials in the experiment, 100 each of CS+ and CS- and 80 of CSneut. The whole experiment will last a total of ~28.5 min. After the first ten CS+ stimuli that will be presented and paired on each occasion with reward, in 20 out of 90 subsequent CS+ presentations, the reward will be omitted (CS+ omit). Further, in 20 presentations of the CS-, a reward will be unexpectedly delivered (CS- unexpected). The CSneut condition will be primarily included to provide a low valence rinse for the glucose taste during the experiment. The order of presentation of events will be randomized and presented to subjects using E-Prime (Psychology Software Tools, Pittsburgh, PA).

fMRI Design

Taste Reward Task: An event-related design will be used. The fMRI variables of interest are percent signal difference after: 1) taste stimulus within subject groups and across taste stimulus types, 2) within subject groups and stimulus type across expected and received vs. expected but not received stimulus, and 3) across groups within stimulus types and conditions as above.

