Acquisition of images: Studies will be performed with a 3T GE MR system (GE Healthcare, Milwaukee, WI) using a standard quadrature head coil. A high-resolution, T1-weighted 3D anatomical scan will be acquired for each subject (IR-SPGR, TR=9 ms, TE=1.9 ms, TI=500 ms flip angle=10°, matrix= 256×256, FOV=220 mm², 124 1.7 mm thick coronal slices) for coregistration to functional data. Functional images were acquired with a gradient-echo T2 Blood Oxygenation Level Dependent (BOLD) contrast technique, with TR=14000 ms (as a clustered volume acquisition of 2000 ms, plus an additional 12000 ms silent interval), TE=30 ms, FOV=220 mm², 642 matrix, 31 slices, 4 mm thick, no gap, angled parallel to the planum sphenoidale. Additionally, one IR-EPI (TI=505 ms) volume was acquired to improve coregistration between EPIs and the IR-SPGR. Head motion will be minimized with a VacFix headconforming vacuum cushion (Par Scientific A/S, Odense, Denmark). MR-compatible goggles (Resonance Technology, Inc, CA, USA) will be used for visual stimuli.

fMRI Image Analysis Pathway: Images will be preprocessed and analyzed using SPM12 (www.fil.ion.ucl.ac.uk/spm/). Images will be realigned to the first volume, normalized to the Montreal Neurological Institute template, smoothed at 6mm full width at half maximum Gaussian kernel. Data will be preprocessed with slice time correction and modeled with a hemodynamic response convolved function using the general linear model, including temporal and dispersion derivatives. A 128-second high-pass filter will be applied for low-frequency BOLD signal fluctuations, and motion parameters as first-level analysis regressors.

Description of how hypotheses will be tested, including neurocomputational modeling approaches. This study tests the brain response in controls compared to ILL AN women. The paradigm will test reward-learning related brain activation in response to taste stimuli. There will be a primary and a secondary analysis pathway in the paradigm.

The primary analysis pathways will use the methods described in the above fMRI analysis pathway sections. For the taste paradigm this primary analysis will identify brain region activation in response to the conditioned fractal or unconditioned sweet taste application as well as brain response when no taste is received but expected. Main effect results will be obtained for condition and subject group, as well as time activity curve

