where α = learning rate. We will assign six time points to each trial and use each subject's individual event history as input. On each trial, the CS (visual fractal) will be taken to be delivered at time point 1, and the UCS reward (sweet taste stimulus) will be delivered at time point 3. We will, as in O'Doherty (O'Doherty et al., 2003), use as learning rate of the model (α) two values for α : a lower learning rate ($\alpha=0.2$) and a higher learning rate ($\alpha=0.7$). In the original study the lower learning rate modeled best brain activation in the ventral striatum and orbitofrontal cortex. The temporal difference error $\delta(t)$ will be created for the CS and the positive and negative UCS for each time-point and an ideal activation curve will be created and convolved with the hemodynamic response curve. That curve will then be modeled to the functional magnetic resonance imaging data in order to generate brain regions that respond according to the model. Time activity curves will then be created in order to compare actual with predicted brain response over time. We cannot predict whether anorexia nervosa women will have simply reduced brain response to the stimuli or if a different learning rate will apply and explain altered learning response. This will be an empirical task during data analysis.

Reversal Learning Paradigm. We adapted a probabilistic reversal paradigm from Cools et al. (Cools et al., 2002). This task has been associated with DA D2 receptor function (Jocham et al., 2009), which is why we selected it for this study design. On each trial, subjects are presented simultaneously with two abstract visual patterns in the left and right visual fields (location randomized). On each trial, the same two patterns are

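### The taste task's stated expectation contrast cannot separate prediction error from sucrose delivery, and the plan does not say which measure tests the prediction-error hypotheses

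*Combined protocol and SAP*

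**What the plan says.** All references are to Section 9 of the combined protocol and SAP unless stated.

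- **fMRI Design, Taste Reward Task** lists three variables of interest. The second is the difference "within subject groups and stimulus type across expected and received vs. expected but not received stimulus". The other two compare taste types within groups, and groups within those types and conditions.
- **Method of Taste Application** gives the trial counts: "There will be a total of 280 trials in the experiment, 100 each of CS+ and CS- and 80 of CSneut". The first ten CS+ trials are all rewarded, and sucrose is then withheld on 20 of the remaining 90. Surprise rewards come on the other cue: "in 20 presentations of the CS-, a reward will be unexpectedly delivered". The neutral fluid is described mainly as a rinse.
- **Taste fMRI** states that "the subjects will be trained to perform one tongue motion after each application of taste stimulant", and that the fluid is swallowed after it is given.
- **Description of how hypotheses will be tested** has the primary pathway identify activation to the fractal and to the "unconditioned sweet taste application as well as brain response when no taste is received but expected". The first-level terms named under the image analysis pathway are HRF derivatives, a high-pass filter and head-motion parameters.
- **Use of mathematical models**, in the secondary pathway, defines a TD error from each subject's event history, with discount factor 0.99 and learning rates 0.2 and 0.7. On fitting it says: "That curve will then be modeled to the functional magnetic resonance imaging data".
- **Section 6** states Hypotheses 1.a (the label is used under both Aim 1 and Aim 2) and 3 as drug effects on PE response in ventral striatum and insula.

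**The concern.** A PE measure should change with surprise while the physical stimulus is held fixed. Received versus omitted sucrose changes both at once. If that contrast, or a TD slope fitted without a delivery term, is what reaches the region-of-interest analysis, a change in plain taste response, tongue movement or swallowing can be reported as a change in PE. PE is the construct named in the hypotheses and in the project title, so a positive result could not be attributed to it. The plan gives two candidate measures and assigns neither to a hypothesis.

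**Working it through.** **1. Trial cells.** 100 + 100 + 80 = 280 trials; at 6 s each this is 28.0 min, against the stated 28.5 min or so. CS+ received: 100 − 20 = 80. CS+ omitted: 20. CS- unexpected: 20. CS- with no taste: 80.

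**2. What the stated contrast compares.** As specified, sucrose, tongue motion and swallow occur in 80 of 80 received trials and 0 of 20 omitted trials. The outcome error is δ = r + γV(next) − V(now). Both trial types share the same cue, so at a given learned value the V terms cancel and δ(received) − δ(omitted) = 1 − 0 = 1. The PE difference therefore coincides with delivery.

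The sensory-motor share of the contrast cannot be computed from the documents. If the sensory-motor effect is assumed to be 0.5, 1 or 2 times the PE effect, the share is 0.5/1.5 = 33%, 1/2 = 50% or 2/3 = 67%.

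**3. The TD error.** The plan's model was simulated with six time points, cue at point 1, reward at point 3, γ = 0.99 and random trial orders after ten initial rewarded CS+ trials. Results are at event level, before HRF convolution.

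| | α = 0.2 | α = 0.7 |
|---|---|---|
| Correlation of outcome δ with sucrose delivery, all 280 trials | 0.69 | 0.57 |
| Same, CS+ and CS- trials only | 0.77 | 0.65 |
| Same, CS+ trials only | 0.93 | 0.80 |
| PE slope shown by a region that responds to sucrose only, with no delivery regressor (multiple of its taste response) | 0.90 | 0.65 |
| SE inflation when a sucrose regressor is added, 1/√(1 − r²) | 1.39 | 1.22 |

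The last row uses the less rounded correlations: 1/√(1 − 0.694²) = 1.39 and 1/√(1 − 0.575²) = 1.22. The slope row is a conditional worst case, not an expected bias.

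**4. Which comparisons are exposed.** Write the measured contrast as C = P + M, with P for prediction error and M for taste and motor response.

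- Drug versus placebo within subject: (P_drug − P_plac) + (M_drug − M_plac). The second term is zero if M is constant across sessions.
- Hypothesis 3, a difference of those differences between groups: a fixed group difference in M also cancels. Bias needs a drug effect on M that differs between groups.
- Plain group comparison of PE level: (P_AN − P_HC) + (M_AN − M_HC). Nothing cancels. Statistical Power expects to replicate elevated PE, which is a comparison of this kind.

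**5. Delivery-matched contrasts from existing trials.**

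- CS- unexpected minus CS+ received (sucrose in both): mean δ difference +0.57 (α = 0.2) or +0.60 (α = 0.7).
- CS+ omitted minus CS- no taste (fluid in neither): −0.60 or −0.59.
- Combined PE separation: 0.57 + 0.60 = 1.17, or 0.60 + 0.59 = 1.19, with no net delivery difference. Received minus omitted gives about 1.0, fully confounded.

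These contrasts compare different cues shown a fixed 3 s earlier. With a canonical HRF and outcome regressors only, a region coding the full TD error shows a positive-PE contrast of only about 0.2 to 0.3. With cue regressors in the model it returns to about 0.5 to 0.6.

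**The case against.** The strongest reply is that the plan never labels received-versus-omitted as prediction error. Its only operational definition of PE is the TD error, which is built for positive and negative outcomes from each subject's events and so includes the 20 unexpected deliveries. This stands. A reader might infer that the confounded contrast is the plan's single PE measure, or that surprise deliveries are ignored throughout; the documents support neither. What remains is that the TD error is labelled secondary and that no hypothesis is tied to either measure.

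It can also be said that the primary pathway estimates the response to sweet taste, so delivery is a modelled event there, and that the TD section defers to a published description of the paradigm that may contain the missing terms. That is possible, but whether a delivery regressor sits beside the TD error is not stated.

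A reader might infer that any difference in taste response between patients and controls would pass for a PE finding under the hypotheses. Step 4 shows otherwise: effects constant across sessions cancel in Hypotheses 1.a and 3. A reader might also infer that the insula is the region worst affected. The documents name it as a hypothesised region but say nothing about how strongly it responds to taste or oral movement.

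Finally, the contrast as written does hold the cue constant, which the matched contrasts do not. That is a real cost of switching and is why cue regressors belong in the fix.

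**Conclusion.** The concern holds in a limited form and should be fixed before analysis. The stated expectation contrast is fully confounded with sucrose, tongue motion and swallowing. The TD error is partly confounded, correlating with delivery at about 0.69 or 0.57 over all trials, unless delivery is modelled. The plan does not say which measure tests Hypotheses 1.a and 3.

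The drug hypotheses are biased only if a drug changes taste or oral-motor response, or changes it differently in the two groups. The documents give no size for this. They list excessive salivation and tongue and face twitches for ongoing amisulpride use, but expect at most nausea after a single dose, so the possibility is neither excluded nor established. Plain group comparisons of PE level are exposed without this condition.

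The figures assume the simulated trial order and event-level regressors; convolution and sampling will change them. The acquisition text gives a 14 s TR, about 122 volumes in 28.5 min, while the syringe-pump text puts scanning in the 3 s between samples. These statements must be reconciled before anyone can judge how well cue and outcome can be separated. This is a pilot and no data are lost, so the point is one that should be fixed rather than one that blocks the study.

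**What to change.** In Section 9, from fMRI Design to Use of mathematical models, name the PE measure for Hypotheses 1.a (both aims) and 3 as one of:

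1. the TD error, fitted in a first-level model that also contains regressors for sucrose delivery, neutral-fluid delivery and each cue (CS+, CS-, CSneut), with the region-of-interest PE estimate taken from that model; or
2. two delivery-matched contrasts, CS- unexpected minus CS+ received (positive PE) and CS+ omitted minus CS- no taste (negative PE), estimated with cue regressors in the model because the cues differ.

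Report received versus omitted only as a combined taste-and-expectation contrast.

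The cost is wording and first-level modelling; no new scans are needed. Under option 1, at equal residual variance, the sucrose regressor alone raises the standard error of the PE slope about 1.39-fold (α = 0.2) or 1.22-fold (α = 0.7) at event level; cue regressors may add to this. Under option 2, each contrast rests on 20 surprise trials per session.

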direction depending on if the pump refills the syringes or pumps solution to the subject. For solution delivery, the tastant is then pressed into the Teflon tubes that are directed toward the subject. The delivering tubes are approximately 10 meters (m) in length and will be pre-filled with sample solutions so that 1.0cc of solution can be administered to the subject in 1 second. There will be 3 seconds between samples during which fMRI scanning will be performed. The syringe pump will be located in the MRI-technician room, and the tubing to the subject will run from the pump to the subject in the MRI scanner room through a port in the wall of the MRI scanning room. The syringe pump's hardware will be connected to a Laptop PC (Dell600, Dell, USA) in the technician room. This PC will control the rate of administration of the solution and the solution choice and will also be the interface between taste application/syringe pump and the MRI scanner control panel. We will use E-Prime (Psychology Software Tools, Inc., Pittsburgh, PA) software in order to coordinate the taste stimulation and fMRI scanning procedure.

Method of Taste Application

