data that illustrate brain activation over time in response to the individual stimulus. *The secondary analysis pathway* includes mathematical models that try to bridge brain function and actual behavior. Computational modeling tries to explain a real world problem in a simplified model that then gets translated into a mathematical equation that can be used to correlate with brain imaging results. This serves the purpose of predicting brain response following a stimulus and depending on factors such as learning rate and received reward, different brain regions will be implicated. That is, the subject performs a specific task or Reward Paradigm and learns under what conditions reward occurs (Figure 3.5). The time course of reward experience is known by the experimenter. In the taste experiment, reward delivery or omission is part of the paradigm and recorded by the stimulus-applying computer.

[figure not shown]

Figure 3.5. Practical application of computational modeling of fMRI data.

Use of mathematical models and testing of alternate models. Taste paradigm: For this paradigm we will use the temporal difference model as described in the past in the original description of this paradigm (O'Doherty et al., 2003). On each trial, the predicted value (V) at any time t within a trial is calculated as a linear product of the weights w_i and the presence or absence of a CS

stimulus at time t , coded in the stimulus representation vector $x_i(t)$:

Learning occurs by updating the predicted value of each time point t in the trial by comparing the value at time $t+1$ to that at time t , leading to a prediction error or $\delta(t)$:

where $r(t)$ = reward at time t . The parameter γ is a discount factor, which determines the extent to which rewards that arrive earlier are more important than rewards that arrive later on. Similar to O'Doherty's study (O'Doherty et al., 2003), we will set $\gamma=0.99$. The weights w_i will be then updated on a trial-by-trial basis

$$\Delta w_i = \alpha \sum_t x_i(t) \delta(t)$$

according to the correlation between prediction error and the stimulus representation:

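### The only functional MRI sequence in the plan (one 2 s volume every 14 s) contradicts the taste-task timing and, if run as written, would more than double the first-level standard error relative to continuous scanning

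*Combined protocol and SAP*

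**What the plan says.** All of this is in Section 9, Research Design and Methods.

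- **Acquisition of images.** The functional sequence is "TR=14000 ms (as a clustered volume acquisition of 2000 ms, plus an additional 12000 ms silent interval". No task is named, and no other functional TR appears for either task. The sentence is in the past tense ("Functional images were acquired with a gradient-echo T2 Blood Oxygenation Level Dependent (BOLD) contrast technique"), although the paragraph around it is in the future tense.
- **Syringe Pump Assembly.** Each sample is delivered "so that 1.0cc of solution can be administered to the subject in 1 second", and "There will be 3 seconds between samples during which fMRI scanning will be performed".
- **Method of Taste Application.** The taste follows the cue by 3 s. Then: "After a further 3 s, the next trial will be scheduled". There are 280 trials, including 20 omitted rewards and 20 unexpected rewards, and "The whole experiment will last a total of ~28.5 min".
- **Planned outputs.** The primary pathway includes "data that illustrate brain activation over time in response to the individual stimulus". For the prediction-error model: "Time activity curves will then be created in order to compare actual with predicted brain response over time". The first-level model includes temporal and dispersion derivatives.
- **Reversal Learning Paradigm.** There are three blocks of about 8.5 min, with inter-stimulus intervals averaging 3.2 s. No sequence is given for this task.
- **Study Visits 1–3.** Each allows about 1 hour for the scan.

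**The concern.** The scanner can follow only one of these descriptions. If it is set to the 14 s cycle, it is silent for 12 s at a time, which is two whole taste trials, and most trials get no volume of their own.

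The region-of-interest estimates for both tasks (Data Storage and Data Analysis Plan) come from the first-level models. They carry the imaging parts of hypotheses 1.a and 1.b under Aims 1 and 2, and hypothesis 3. A loss at acquisition would affect every participant in all three sessions and could not be recovered in analysis. Statistical Power also names learning the data's distribution and standard deviation for future studies as a main goal, and extra first-level noise would inflate those standard deviations. The plan states no gain from sparse sampling that would offset this.

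**Working it through.** **1. Reproduce the stated duration.** Trial length = 3 s + 3 s = 6 s. 280 × 6 s = 1,680 s = 28.0 min, against about 28.5 min (1,710 s) stated. The 6 s trial is therefore the intended timing. The alternatives do not reproduce the figure: 280 × 4 s (1 s delivery plus a 3 s gap) = 18.7 min, and 280 × 7 s = 32.7 min.

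**2. Set the sequence against that timing.**
- 14 / 6 = 2.33 trials per TR.
- One volume per trial needs 280 × 14 s = 65.3 min. The scan is 60 min and must also hold 3 × 8.5 = 25.5 min of reversal blocks.
- With task and scanner started together, 80 of the 280 three-second intervals after the outcome overlap any acquisition, and 40 contain a complete 2 s volume.
- With 6 s trials and 1 s delivery, samples on consecutive trials are 6 − 1 = 5 s apart, not 3 s.

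**3. Count taste volumes (1,710 s).** TR 14 s: 1,710 / 14 = 122. TR 3 s: 1,710 / 3 = 570. TR 2 s: 1,710 / 2 = 855. The 3 s and 2 s comparators are assumptions; the documents state neither.

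**4. Coverage of the rare events.**
- Of the 40 omissions and unexpected rewards, the expected number with a volume 4–7 s after the outcome is 40 × 3/14 = 8.6. The range is 5.7–11.4 by scanner start offset at 6.0 s spacing.
- Volumes per 2 s bin of a time-activity curve = events × 2 / TR. For the 20 omissions: 20 × 2/14 = 2.9, against 13.3 at TR 3 s and 20 at TR 2 s. For the 80 rewarded CS+ trials: 80 × 2/14 = 11.4.

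**5. First-level precision, taste task (simulation).** The model has five trial types at outcome, the SPM canonical response with both derivatives, the 128 s filter, six motion regressors and a constant. At TR 14 s the design is 122 × 48 and of full rank. Noise per volume is equal across TRs, with assumed autocorrelation from 0 to 0.7 at 2 s lag.

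| Standard error at TR 14 s relative to | Trial-type contrasts | Prediction error (learning rate 0.2) |
|---|---|---|
| continuous TR 3 s | 2.1–2.6 | 2.2–2.6 |
| continuous TR 2 s | 2.2–3.2 | 2.4–3.1 |
| one volume locked to each 6 s trial (280 volumes) | 0.11–0.42 | 0.94–1.42 |

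A simpler model (canonical response only, unexpected reward minus omission) gives 2.3–2.4 against TR 3 s and 2.5–2.9 against TR 2 s. An assumed 30% signal-to-noise gain per volume from the longer TR brings the low end to 2.1 / 1.3 = 1.6.

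**6. Reversal task, if this sequence is used.** 510 / 14 = 36 volumes per block (510 / 2 = 255 at TR 2 s). If blocks are modelled separately, the parameters are 4 event types × 3 basis functions + 6 motion + 7 filter terms + 1 constant = 26, fitted to 36 volumes. No stable standard-error ratio can be given.

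**The case against.** **The 14 s line may be leftover text.** The past tense suggests it was carried over from another study, so it may never be run and every stated harm is conditional. That is a fair inference, but the visible text does not say so. If it is true, the plan states no valid functional TR for either task, which needs the same correction.

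**The comparator is not the plan's.** This stands. The contradiction needs no comparator, but the size of the loss does. Another reading of the syringe-pump text is one volume locked to each trial. Against that reading the 14 s sequence is better for trial-type contrasts with the planned derivatives, and about equal for prediction error. Without the derivatives the comparison reverses: the 14 s standard error is about 1.3–2.2 times the locked one.

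**The ranges are not bounds.** This also stands. Repeat simulations of the outcome-only model at 6.1 s spacing without autocorrelation reached 2.8–2.9 (TR 3 s) and 3.4–3.6 (TR 2 s). Adding regressors for the fractal cues at 6.1 s gave 2.8–2.9 and 3.4–4.6; at 6.0 s spacing it made the 14 s design numerically rank-deficient. All of these make the loss larger.

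**The effect on conclusions is not shown.** The same sequence would apply to all drugs and both groups, so the loss is in precision and no bias in drug–placebo contrasts is claimed. Aims 1 and 2 are framed as feasibility and acceptability. Both points are correct and limit the claim, but the imaging hypotheses still depend on these estimates.

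**Two details are weaker.** The 5 s against 3 s mismatch is loose: the 3 s may be the interval from taste to next trial, and most CS− trials deliver nothing. The sequence also sits within the taste-task text, so applying it to the reversal task is conditional.

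**Conclusion.** The concern holds: the sequence is wrong as written and must be corrected before scanning. The contradiction between the 14 s cycle, scanning between samples and 6 s trials rests on the documents' own figures and is certain, subject to the figures not shown, whose timing could not be checked.

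The size of the loss is conditional on the sequence being run as written and on continuous scanning at TR 2–3 s as the comparator. With equal noise per volume, taste-task standard errors would be a little over two to about three times as large, or about 1.6 times at the low end if the longer TR brings the assumed signal gain. Averaged event effects and time-activity curves would remain estimable but much less precise.

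The effect on group-level power cannot be computed, because the documents do not give the share of variance that is first-level noise. Behavioural reversal learning, feasibility and acceptability are unaffected.

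**What to change.** Reconcile the four places in Section 9 that bear on timing: Syringe Pump Assembly, Method of Taste Application, Acquisition of images, and Reversal Learning Paradigm. Replace the 14 s sparse sequence with an acquisition stated separately for each task: TR, any silent interval, volumes per run, and how volumes relate to trial onset.

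One workable example is continuous imaging at about the 2,000 ms volume time already given, which yields about 855 taste volumes and 255 per reversal block. One volume locked to each taste trial is not an adequate substitute while the derivatives stay in the model; choosing it would mean revising the first-level model too. If sparse sampling is really intended, say why, and revise the task timing, time-activity curves and reversal contrasts to match it.

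The cost is corrected text and scanner settings. No extra scan time, visits or participants are needed.
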